4.4.2. Handling of Missing Data/Imputation/Censoring Rules

For the primary efficacy endpoint, defined as mean fibrosis % from baseline to 12 months of therapy, as well as for the key secondary endpoint (MRI) different multiple imputation approaches will be applied to handling missing data. Further details on the missing imputation strategies are provided in Section 6.3.1 of the present document for the primary efficacy endpoints, and in Section 6.3.2.2 and 6.3.2.3 for the key secondary endpoints.

Results for the other efficacy and safety endpoints will be based on non-missing data only (i.e. missing observations will not be replaced).

4.4.3. Handling of Drop-Out Patients

Patients will be included in each analysis based on available assessments. Sensitivity analyses will be performed in order to evaluate the influence of missing data: further details on the missing imputation strategies are provided in Section 6.3.1 of the present document for the primary efficacy endpoints, and in Section 6.3.2.2 and 6.3.2.3 for the key secondary endpoints.

5. ANALYSIS POPULATIONS

On the basis of the study protocol, the following analysis populations will be defined:

- Intent-To-Treat Analysis (ITT) Set: it comprises all patients to whom study
 treatment has been assigned by randomization and who received at least one dose
 of study medication. According to the intent to treat principle, patients will be
 analyzed according to the treatment they have been assigned to during the
 randomization procedure. The ITT set will serve as the basis for the analysis of
 efficacy.
- Per Protocol (PP) Set: it consists of a subset of patients in the ITT who had no major
 protocol deviation. Protocol deviations leading to exclusion from the PPS will be
 defined in a separate document. The PP set will serve as supportive analysis of the
 primary endpoint.

Sponsor: ITALFARMACO Protocol: DSC/15/2357/53

- Safety (SAF) Set: it consists of all patients who received at least one dose of study
 medication. Patients who have been randomized and did not take at least one dose
 of study medication will not be included in the safety set. Patients will be analyzed
 according to the study treatment they actually received. This analysis set will be
 used for the analysis of safety.
- Pharmacokinetic (PK) Set: it consists of all randomized patients who have received at least one dose of study treatment and have at least post-baseline PK sample.

6. STATISTICAL METHODOLOGY

6.1. Study Patients

A complete description of screening disposition will be performed overall on screened patients (i.e. patients who provided a valid Informed Consent Form) summarizing the number of patients who complete the screening phase and the primary reason for screening failure.

A description of patients' disposition will be also provided on enrolled patients (i.e. screened patients who completed the screening phase), specifying the number of randomized patients, the number of patients at each visit, the number of completed and discontinued patients and the reason for the discontinuation.

The analysis populations will be described and the reasons for excluding a patient from any particular population will be provided with the number of protocol deviators per each criterion. Protocol deviations, including COVID-related protocol deviations, will be summarized by treatment for the randomized patients.

Non-protocol deviations will be also summarized on randomized patients. The list of Non-protocol deviations for this study is listed in Table 6.1-1:

Table 6.1-1: List of non-protocol deviations

Deviation code	Description	Exclusion from analysis population	
NOPD01	Patient who did not take at least one dose of the	ITT/PP/SAF/PK	
	study treatment		

NOPD = Non-protocol deviations.

6.2. Background and Demographic Characteristics

All data about patient demographics and baseline characteristics will be summarized on the ITT and PP set overall and by treatment group by means of summary descriptive statistics.

Sponsor: ITALFARMACO
Protocol: DSC/15/2357/53

Demographic characteristics will include sex, age, ethnicity and race. The patient's age will be computed as the time in years between the date of birth to the date of the informed consent signature.

Baseline characteristics will include time from diagnosis, DMD mutation (deletion, duplication, point mutation) and Mutated exon(s) data (Exon 45, Prior to exon 45, Post-exon). Time from diagnosis to informed consent will be computed as years elapsed from diagnosis to informed consent, plus one day.

Medical history data will be presented as the number and percentages of patients with at least one pathology. Condition will be presented by System Organ Class (SOC) and Preferred Term (PT) according to the MedDRA dictionary.

6.3. Efficacy Evaluation

The efficacy analyses will be performed on patients valid for the ITT population and will be presented by planned treatment group. The primary efficacy endpoint will be also analyzed on the PP population for supportive purpose.

6.3.1. Primary efficacy analysis

Definition of primary endpoint

The primary endpoint is the mean change in total fibrosis comparing the histology of muscle biopsies before and after 12 months of treatment with givinostat versus placebo. The primary efficacy assessment for this study is the Total Fibrosis assessed through histological examination of muscle biopsies. A muscle biopsy was collected at the beginning and at the end of treatment to calculate the mean change from baseline to 12 months.

For each patient, the percentage of total fibrosis will be calculated as a mean of available fields at each evaluation.

Analysis methodology

The primary hypothesis to be tested is that total fibrosis (%) will increase less in the givinostat group than in the placebo group.

Since the blinded data at the time of the sample size re-estimation indicated the primary efficacy variable to be non-Normally distributed, the change in mean fibrosis from baseline to endpoint after 12 months of therapy will be analyzed on the log scale. Therefore, mean fibrosis at baseline and Visit 11 will be log transformed prior to analysis. An analysis of covariance (ANCOVA) model will be fitted to the data with the difference between log visit 11 and log baseline values as the dependent variable; log baseline value will be included as covariate and treatment and concomitant steroid use at baseline as independent class variables. LSmean values for the log change from baseline to visit 11 will be extracted, together with the associated log scale SEs; the difference in LSmean values will also be extracted as the measure of treatment effect along with corresponding log scale SE and two-

Sponsor: ITALFARMACO
Protocol: DSC/15/2357/53

sided 95% Confidence Interval (CI). LSmean values, the difference in LSmean values and the associated CI will be back transformed to the ratio scale for the purpose of presentation.

Summary descriptive statistics (N, geometric mean, %CV, mean, median, SD, min and max) for total fibrosis value and change versus baseline, at each time point, will be provided.

A Mixed Model will be fitted to the data with the difference between log visit 11 and log baseline values as the dependent variable; log baseline as a covariate, treatment will be included as independent class variables and treatment by sequence interaction. The sequence of biopsy site (Right-Left, Left-Right) will be included as a fixed effect and subject as a random effect to evaluate the difference in Total Fibrosis between biopsy sites.

If the treatment by sequence interaction is p>0.10, then the model without the interaction term will be presented.

Data handling rules

Primary analysis will be based on observed data only.

Sensitivity analysis for the primary endpoint will be performed as follow:

- 1. Multiple imputation for missing data:
 - a. Missing baseline primary endpoint data will be imputed as the geometric mean of all non-missing baseline primary endpoint values across the randomized treatment groups. Visit 11 missing data will be imputed (on the log scale) under a Missing At Random (MAR) assumption using SAS procedure MI within each treatment group using distribution implied by the non-missing patient data for that treatment group. A total of 20 imputation runs will be performed. Post imputation, each imputed dataset will be analysed separately exactly as described for primary efficacy analysis. The SAS procedure MIANALYZE will then be used to combine the 20 datasets of estimates by Rubin's rules. The resulting multiply imputed means and difference in means will be presented, along with the associated SEs, 2-sided 95% CIs and 2-sided p-values.
 - b. Missing baseline primary endpoint data will be imputed as the geometric mean of all non-missing baseline primary endpoint values across the randomized treatment groups. Visit 11 missing data will be imputed (on the log scale) under a Missing Not At Random (MNAR) assumption using SAS procedure MI for both randomized treatment groups using the distribution implied by the non-missing patient data within the placebo group. A total of 20 imputation runs will be performed. Post imputation, each imputed dataset will be analysed separately exactly as described for primary efficacy analysis. The SAS procedure MIANALYZE will then be used to combine the 20 sets of estimates by Rubin's rules. The

Sponsor: ITALFARMACO
Protocol: DSC/15/2357/53

resulting multiply imputed means and difference in means will be presented, along with the associated SEs, 2-sided 95% CIs and 2-sided p-values.

- 2. An analysis will be conducted as per the primary analysis (including multiple imputations), but on the non-log transformed data.
- 3. Both the log scale and non-log scale analyses of the primary endpoint (excluding the multiple imputations) will be repeated using the PP Set.

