## 8.3 Study Treatment Assignment

Patients will be dispensed the study treatment on an outpatient basis. All study treatment supplies are to be used only for this protocol and for no other purpose.

Patients will be assigned to one of the two treatment arms (givinostat vs. placebo) in a 2:1 ratio. The randomization process will be stratified by the factor related to concomitant steroid use at baseline (yes vs. no).

The randomization numbers will be generated using procedures that ensure that treatment assignment is unbiased. A patient randomization list will be produced using a validated system that automates the random assignment of patient numbers to randomization numbers.

At Visit 3, all patients who fulfill all inclusion criteria and none of the exclusion criteria will be randomized via an Interactive Web Response System (IWRS) to one of the treatment arms. The investigator or his/her delegate will log on to the IWRS, confirm that the patient fulfills all the inclusion/exclusion criteria and enter information relevant to the stratification factor. The IWRS will assign a randomization number to the patient which will be used to link the patient to a treatment arm.

During the study, the Investigator will supply the patient with the appropriate number of suspension bottles sufficient to cover the period between two visits (3 months of treatment).

The Investigator is to use the IWRS at each dispensing visit to obtain the packaging number of the study treatment to be dispensed to the patient. Study treatment should be dispensed by authorized personnel only.

The Investigator will provide the patient with written instructions on the dosage and corresponding volume in milliliters of suspension to be taken at each administration.

17 June 2020 Page 54 of 110

In the unlikely case of system unavailability, the Interactive Voice Response System (IVRS) will be used as backup for randomization and treatment assignment.

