## 9.1.1 Visit 1 and Visit 2 - Screening (Week -4 + 2 weeks)

The Screening visits (Visit 1 and Visit 2) will occur within 4 weeks (± 2 weeks) prior to the Randomization Visit. The following assessments will be performed at Visit 1:

- Written Informed Consent
- Eligibility criteria: review of inclusion and exclusion criteria
- Medical history and demographic data
- Prior medications (taken in the past 6 months)
- Physical examination
- Vital signs (blood pressure, heart rate and body temperature)
- Weight and height
- 12-lead ECG (in triplicate)
- Echocardiogram
- Pulmonary function tests: FEV1, FVC, FEV1/FVC, and PEF
- Blood collection for:
  - serology
  - hematology
  - blood chemistry
  - coagulation tests (prothrombin time [PT] and activated partial thromboplastin time [aPTT])
  - thyroid function tests (TSH, fT3, fT4)
- Urine analysis
- Quality of Life test (SF-36)
- 6MWT + MFM
- Muscle strength test (knee extension and elbow flexion by HHM)
- Time function tests
- AE assessments

17 June 2020 Page 63 of 110

If all inclusion and exclusion criteria have been met and the patient is eligible, an MRI, MRS and muscle biopsy are to be performed before the first IMP dose. At the discretion of the Investigator, patients not meeting inclusion/exclusion criteria may be re-screened twice with an interval of at least 30 days between assessments.

At Visit 1, after having filled in the "Eligibility criteria" section of the eCRF, eligible patients will be randomized to one of the two following muscle biopsy sequences by the system:

V2: Right Arm - V11: Left Arm

V2: Left Arm - V11: Right Arm

The site will receive the muscle biopsy sequence by email.

Randomization will be balanced in a ratio of 1:1 and will not be stratified.

If needed for logistic reasons, Visit 2 can be completed on two different days included in the window period between Visit 1 and Visit 3. Patients will be instructed to avoid physical activity that would exceed their normal activity for 3 days before each visit.

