1.1. Changes from The Study Protocol

The following changes have been made to the statistical methodology planned in the study protocol:

- Total fibrosis (primary endpoint): the main analysis will be based on log-trasformed data.
 Sensitivity analyses will be performed on the original scale and also applying different multiple imputation approaches (both MAR and MNAR)
- MRI (key secondary endpoint): same analysis planned for the primary endpoint
- Other secondary endpoints: statistical analyses will be performed by means of Mixed Model for Repeated Measures instead of ANCOVA
- Total WB dystrophin 1 and Total WB dystrophin 2 will be analyzed
- Difference between biopsy sites at baseline will be evaluated for Total fibrosis, Total CSA and MFA%

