3.3.2. Method of Assigning Patients to Treatment Group

TREATMENT RANDOMIZATION

Approximately 51 eligible patients will be randomized in a 2:1 ratio to be treated with givinostat or placebo for a period of 12 months. The randomization process has been stratified by the concomitant steroids use at baseline (yes vs. no).

Sponsor: ITALFARMACO
Protocol: DSC/15/2357/53

BIOPSY SITES RANDOMIZATION

At Visit 1, after having filled in the "Eligibility criteria" eCRF page, eligible patients will be randomized to one of the two following sequences to assign to the patient:

V2: Right Arm - V11: Left ArmV2: Left Arm - V11: Right Arm

Randomization will be balanced in a ratio of 1:1 and will not be stratified.

PHARMACOKINETIC (PK) SAMPLING RANDOMIZATION

Blood samples for PK analysis of Givinostat and its metabolites should be collected at 4 visits: Visits 5 (Week 4), 8 (Week 12), 9 (Week 24) and 11 (Week 48).

All patients will have a total of 6 PK blood specimens drawn during the study:

- Two samples drawn pre-dose, these 2 specimens must be drawn at 2 different visits;
- One sample drawn between 0 and 2 hours post-dose;
- One sample drawn between 2 and 4 hours post-dose;
- One sample drawn between 4 and 6 hours post-dose;
- One sample drawn between 6 and 10 hours post-dose.

Eight sequences of combinations will be randomly selected from all the possible ones and each sequence of combinations will be randomly allocated to randomized patients in a ratio of 2:1 (Givinostat vs. Placebo).

PK randomization will be stratified according to the treatment group assigned at randomization.

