- Fiber size variability will be calculated at baseline and Visit 11 as the median of the interquartile range (IQR) of total CSA according to the following formula:

Fiber size variability_i =
$$Q_{3i} - Q_{1i}$$

Ver.04 25Jun2020

Sponsor: ITALFARMACO
Protocol: DSC/15/2357/53

where j = patient 1, 2... and Q_1 and Q_3 are the first and third quartile for each patient (calculated among the 4 fields).

- Dystrophin
 - Total WB Dystrophin 1
 - Total WB Dystrophin 2

Analysis methodology

The absolute value of percentage of MFA and change versus baseline, at each time point, will be summarized as a continuous variable using descriptive statistics.

The absolute change in percentage of MFA after 12 months of therapy will be calculated as the difference between percentage of MFA at Visit 11 and its baseline value. This variable will be analyzed using an ANCOVA model with baseline percentage of MFA as covariate and treatment and concomitant steroid use at baseline as independent class variables. Results will be reported as Least-Square Means as well as difference between treatments together with their corresponding two-sided 95% CI. Possible need for log transformation of this variable will be assessed by check of ANCOVA model residuals. If considered non-Normal, a supportive analysis will be performed on the log scale.

The same analyses will be done for the adipose tissue (%), other histological structure, fibers with nuclear centralizations, regenerative fibers, CSA I, CSA II, Total CSA, Fiber size variability and percentage of dystrophin.

Total number of fibers counted in Slide I, II and III will be summarized as a continuous variable at each time point as well as change vs baseline using descriptive statistics.

A Mixed Model will be fitted to the data with the difference between visit 11 and baseline values as the dependent variable; baseline as a covariate, treatment will be included as independent class variables and treatment by sequence interaction. The sequence of biopsy site (Right-Left, Left-Right) will be included as a fixed effect and subject as a random effect to evaluate the difference in Total CSA between biopsy sites. The same evaluation will be done also for MFA %.

If the treatment by sequence interaction is p>0.10, then the model without the interaction term will be presented.

Data handling rules Primary analysis will be based on observed data only.

Sensitivity analyses for the histological endpoints will be performed as follow:

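### The primary ANCOVA leaves out the randomised left/right biopsy order, a conditional loss of precision but not a bias; the separate biopsy-site model needs tidying and does not match SAP 1.1

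*SAP*

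**What the plan says.** Protocol 9.1.1 states that at Visit 1 "eligible patients will be randomized to one of the two following muscle biopsy sequences by the system": right arm at V2 then left at V11, or the reverse. SAP 3.3.2 adds: "Randomization will be balanced in a ratio of 1:1 and will not be stratified". Treatment is assigned separately at Visit 3. Protocol 8.3 says of it: "The randomization process will be stratified by the factor related to concomitant steroid use at baseline (yes vs. no". Nothing therefore balances biopsy order between the treatment groups.

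The primary model in SAP 6.3.1 analyses log V11 minus log baseline fibrosis. Its terms are: "log baseline value will be included as covariate and treatment and concomitant steroid use at baseline as independent class variables". The ANCOVA in Protocol 13.6.1 has no order term either.

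SAP 6.3.1 then gives a second model of the same log change, to evaluate the difference between biopsy sites. It contains baseline, treatment and a treatment-by-sequence interaction, and "The sequence of biopsy site (Right-Left, Left-Right) will be included as a fixed effect and subject as a random effect". Steroid use is not listed. For the interaction: "If the treatment by sequence interaction is p>0.10, then the model without the interaction term will be presented". SAP 6.3.2.3 repeats the structure for total CSA, with "subject as a random effect to evaluate the difference in Total CSA between biopsy sites", and for MFA%.

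SAP 1.1 describes the added analysis differently: "Difference between biopsy sites at baseline will be evaluated for Total fibrosis, Total CSA and MFA".

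**The concern.** If fibrosis differs on average between right and left arms, that difference enters every change score, with its sign set by the biopsy order. The trial randomises order, so it is known for every patient, yet the primary model leaves its contribution in the residual. At stake is some power in a 48-patient comparison, recoverable from data already held.

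The model that does contain order has three loose ends. It has one change per patient together with a random subject effect. It drops the treatment stratification factor. It also gives no rule for turning the sequence coefficient into a side difference. And because it models change, it does not deliver what SAP 1.1 says will be evaluated.

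**Working it through.** **The plan's own figure.** Inputs from SAP 3.5: difference 9 points, SD 10, 32 versus 16, two-sided 5%. The noncentral t gives 79.4% power at 30 + 15 and 82.1% at 32 + 16, so 48 is the smallest 2:1 total that reaches 80%. It reproduces.

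**Log scale (the primary scale).** The documents give no log-scale SD, effect or side difference, so all are assumed: between-patient SD 0.4, per-biopsy SD 0.3, effect -0.35, steroid use 50%, 48 patients. The first figure comes from 8,000 trials per cell, the second from an independent repeat.

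| Right/left ratio (log difference) | Power without order, % | Power with order, % |
|---|---|---|
| 1.00 (0) | 81.6; 82.6 | 80.5; 81.5 |
| 1.11 (0.1) | 79.2; 79.8 | 80.7; 81.2 |
| 1.22 (0.2) | 74.4; 74.3 | 80.3; 80.1 |
| 1.35 (0.3) | 67.6; 68.0 | 80.2; 80.2 |

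In the 8,000-trial run the mean treatment estimate stayed between -0.348 and -0.352, and rejection under the null between 4.9% and 5.4%, with or without order.

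**Points scale.** Let s² be the variance of one biopsy net of side (taken as equal at both visits), β the slope of V11 on baseline and d the side difference.
- Residual variance without order: V - C²/V, where V = s² + d²/4 and C = βs² - d²/4.
- Residual variance with order: s²(1 - β²).

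Take SD 10 as the residual SD without order. For β = 0.5 and d = 3, s² = 126.7, V = 128.95 and C = 61.10. Then 128.95 - 61.10²/128.95 = 100.0, and with order 126.7 × 0.75 = 95.0. The power with order loses one degree of freedom. It is also averaged over chance imbalance: the variance is multiplied by 1/(1 - r²), r being the treatment-order correlation, over the hypergeometric distribution of 24:24 orders with 16 on placebo.

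| β | d | Variance with order | Power without to with, % | Gain, points |
|---|---|---|---|---|
| any | 0 | 100 | 82.1 to 81.2 | -0.9 |
| 0.5 | 3 | 95.0 | 82.1 to 83.1 | 1.0 |
| 0.5 | 5 | 86.7 | 82.1 to 86.3 | 4.3 |
| 0.5 | 7 | 75.4 | 82.1 to 90.6 | 8.5 |
| 0 | 3 | 97.8 | 82.1 to 82.0 | about 0 |
| 0 | 5 | 94.1 | 82.1 to 83.4 | 1.4 |
| 0 | 7 | 89.2 | 82.1 to 85.3 | 3.3 |

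**Chance imbalance.** With 24:24 orders, the share having a given order can differ between treatment groups only in steps of 9.375 percentage points. A difference of 18.75 or more occurs in 36% of trials, and of 28 or more in 12%.

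**Random subject effect.** In one simulated data set with one change per patient, the REML log-likelihood was 14.4511 whether subject variance was set to 0, 25, 50, 75 or 99% of the total. The data cannot divide it from the residual.

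**What the sequence coefficient means.** Let d be right minus left. R-L patients, compared with L-R patients, are d higher at baseline and d lower at V11. Given baseline, the coefficient is -d - βd = -(1 + β)d. This requires the same d at both visits; otherwise it is -(d₁₁ + βd₂), where d₁₁ and d₂ are the side differences at V11 and V2. Because the SAP models change, the fitted baseline coefficient is β - 1, so β is that coefficient plus 1.

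**Power of the site checks.** Same assumed log-scale setting, differences 0.1/0.2/0.3: the SAP's sequence term detects 29/79/98%, and a baseline-only right-versus-left contrast 10/27/51%. The interaction screen at p 0.10 detects interactions of 0.20/0.35/0.50 in 21/40/64% of trials.

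**The case against.** The strongest reply is that this is a modelling preference which the SAP already covers. Order did not stratify treatment, so nothing in the design obliges the primary model to carry it. The second model in SAP 6.3.1 will give an order-adjusted treatment effect on the same log change. No side difference is documented, every gain above rests on assumed inputs, and with no side difference the extra term loses power. The points-scale figures do not describe the log-scale primary test. Charging the order term only one degree of freedom, without chance imbalance, would also flatter it: at β = 0.5 and d = 3 the gain would read 1.8 points rather than 1.0.

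Most of this stands, and it is why the point is a suggestion. What it does not answer is that the order-adjusted model is presented as a site check, omits steroid use and does not carry the primary inference.

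On SAP 1.1, the first biopsy site determines the sequence, so the phrase about baseline could be read as naming the grouping factor. That makes it ambiguous, and one line would settle it.

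A reader might infer that omitting order biases the treatment effect or inflates type I error. It does neither: order is randomised independently of treatment, and the simulations agree. A reader might also infer that the site model is invalid. Its fixed-effect estimates stand and it does test for a side difference; the random effect is redundant rather than harmful to them.

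**Conclusion.** The point holds as a modest, conditional improvement to the primary model, plus a tidying of the site model and a wording conflict within the SAP. The validity of the primary test is not in question.

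The size depends on a side difference that the documents do not give. On the assumed log-scale inputs, adding order costs about 1 point of power when the arms are alike, gains 1 to 2 points at a ratio of 1.11, and gains about 6 and 12 points at 1.22 and 1.35. On the points scale with SD 10 as the residual SD, the gain at d = 3, 5 and 7 is about 1.0, 4.3 and 8.5 points for β = 0.5, and about 0, 1.4 and 3.3 for β = 0. For small side differences the benefit is negligible.

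The unidentifiable random effect, the missing steroid term and the mismatch between SAP 1.1 and the methods sections need no numerical assumption.

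**What to change.** **(a) Primary and histology ANCOVAs.** Add biopsy sequence (R-L versus L-R, as randomised) as a main-effect class variable, and carry it into the multiple-imputation analyses. The cost is SAP wording, one degree of freedom and about 1 point of power if there is no side difference. The term will cost more in the small genotype and exon subgroups of SAP 6.5. No new data are needed.

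**(b) Site model in SAP 6.3.1 and 6.3.2.3.** Either drop the random subject effect and add steroid use, or use two records per patient with visit, treatment by visit, arm biopsied, steroid use and a random subject effect. In either case state the assumption that the side difference is the same at both visits. If the sequence coefficient is converted by dividing by -(1 + β), state that β is the fitted baseline coefficient on change plus 1. Keep the treatment-by-sequence check as supportive only, and acknowledge its low power.

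**(c) SAP 1.1.** Reconcile it with 6.3.1 and 6.3.2.3, either by removing the reference to baseline or by adding a baseline right-versus-left contrast with its lower power stated.
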